Study Protocol and Statistical Analysis Plan (SAP)

Official Title: The Crohn's Disease Exclusion Diet With Early Dairy Introduction Plus Partial Enteral Nutrition (CD-EDEN) in Adult Patients With Crohn's Disease

Unique Protocol ID:605/16-12-2021

(NCT ID not yet assigned)

Date: 24/08/2022

Study Protocol

Background

Crohn's disease (CD) is a chronic relapsing inflammatory bowel disease (IBD), that may affect any part of the gastrointestinal tract, but most commonly the terminal ileum and colon. Its clinical manifestations usually include diarrhea, abdominal pain, fatigue, and unintentional weight loss. CD has a significant impact on patients' quality of life (1).

The incidence of IBD has markedly increased in the Western world during the 20th century, in parallel with the urbanization and industrialization of societies. At the beginning of the 21st century, the incidence started to increase in newly industrialized countries too, suggesting the role of environmental factors in IBD emergence (2,3).

Current epidemiological trends indicate that prevalence continues to grow due to decades of high incidence and low mortality, thanks to advances in medical science. In many westernized countries, IBD prevalence exceeds 0.3%, which translates to a high burden of IBD. More specifically, recent data, published in 2021, shows that the incidence of CD in Europe ranged between 0.4 to 22.8 per 100,000 person-years (4), while in Greece the incidence of CD is about 2.0 to 3.6 per 100,000 per year (5). The predicted value of IBD prevalence in the Western world is 1% by 2030, based on forecasting models. Prevalence of IBD in advanced developing countriesis currently low but is expected to rise in the following decades. The evolving global burden of IBD is expected to challenge the health-care systems in managing these complex and costly diseases (2-4).

The disease etiology is complex and not fully understood. Accumulated data indicate that environmental factors, including diet, might play a key role in the pathogenesis and inflammation, through mechanisms involving gut dysbiosis, in genetically susceptible individuals (6).

Epidemiological data suggest that following a Mediterranean diet, which represents the "pre-industrial" dietary pattern, is associated with decreased risk for CD, whereas a Western diet, rich in animal fat, processed foods and food additives, seems to be linked with an increased disease risk (2).

Current evidence-based nutritional guidelines for CD, arise mainly from epidemiological data and generally suggest a "healthy diet", characterized by an increased consumption of nutrient-dense foods along with a restricted intake of saturated and trans-fats, emulsifiers, thickeners, processed foods, unpasteurized dairy. According to the Dietary Guidance from the International Organization for the Study of Inflammatory Bowel Diseases (IOIBD), consensus was not reached for pasteurized dairy consumption among patients with CD. Based to evidence from epidemiology and animal models, the authors clarify that it is prudent for Crohn's disease patients to avoid lactose, given that lactase deficiency and lactose intolerance is common among patients with IBD. It was also noted that it could be prudent to reduce dairy fat and processed dairy rich in maltodextrins and emulsifiers (7). To date, no clear and strong recommendation can be given to follow a specific diet for inducing remission in patients with active CD, whereas the importance of a personalized nutritional approach is highlighted (8). Exclusive Enteral Nutrition (EEN) is the only well-established dietary therapy in CD and is commonly used for the induction of remission in mild to moderate pediatric CD (8-9, 12-13). Evidence according to EEN efficacy in adults is not consistent, which could more likely be explained by the compliance difficulty rather that by mechanistic differences (10-12). It is of interest, that fecal inflammation increases rapidly after food re-introduction following EEN in children (14). In this context, partial enteral nutrition (PEN) has sparked scientific interest as a possible maintenance dietary strategy. PEN has been shown to be beneficial in maintaining remission, but poor compliance due to low formula palatability and patients' fatigue remains an important barrier in the clinical practice. Moreover, PEN is inferior to EEN in inducing remission (13,15). Sigall Boneh and her colleagues evaluated a novel dietary intervention that combined PEN with an elimination diet (19). The Crohn's disease exclusion diet (CDED) is a whole-food, high protein, low saturated fat, low taurine, low heme, low food additives diet with exposure to fiber mainly from fruits, vegetables and complex carbohydrates. More specifically, CDED eliminates specific dietary components hypothesized to induce dysbiosis and appears to be effective in inducing and maintaining remission both in pediatric and adult population (16-19).

Currently, most of the available strategies to meet goals of medical therapy for CD require immune suppression. In the era of newer biological agents, safety and efficacy in managing CD has increased whereas, eventually, most patients require dose escalation and combination therapy to tackle with loss of response, which comes at a higher cost and with increased health risks (22, 23). It has already been shown that CDED plus PEN could be an effective strategy to obtain remission in patients failing biological therapy (17), while a recent pilot study indicated efficacy in using CDED as a dietary monotherapy for induction and maintenance of remission in patients with mild-to-moderate active CD (18). Despite the promising findings, CDED should be further explored in powered randomized controlled trials, including patients with wide disease phenotypes, clinical activity and concurrent drug therapies. Moreover, the exposure to certain of the eliminated foods should be tested in order fortailored nutrition advice to be feasible.

In light of the growing evidence linking diet with CD outcomes and given the patients' strong interest in ways to manage their disease through diet (12,20), the establishment of a palatable and as flexible as possible dietary pattern, not merely for inducing remission, but also as a feasible maintenance strategy is one of the main priorities in CD research at present.

Objectives

The initial hypothesis is that Crohn's disease may occur via an order of events involving dysbiosis and genetically determined or environmentally acquired defects in innate immunity. It has also been hypothesized that the mechanism of EEN for induction of remission acts by the elimination of exposure to dietary components that may cause a defect in bacterial clearance or dysbiosis. Based on that premise, Crohn's Disease Exclusion Diet (CDED), has been developed, as

The aim of this study is to explore the role of the CDED combined with PEN in both inducing and maintaining remission of CD in adults, taking into consideration important objective biomarkers such as faecal calprotectin (FC) (21) along with patient reported outcomes. More precisely, our primary goal is to investigate whether CDED with PEN could lead to a significant decrease in feacal calprotectin concentration. In view of the existing dietary guidelines for adult Crohn's disease patients (7,8) and considering that dairy constitute the main dietary source of calcium, researchers wish to challenge patients in remission with a gradually increasing exposure to dairy products, to assess tolerability, prospecting for the development of a personalized remission maintenance diet based on the CDED principles. Our aim is to examine the proportion of patients with significant feacal inflammation elevation following the dairy introduction.

We intent to investigate the effectiveness and feasibility of this dietary strategy in terms of changes in clinical and biochemical indices, patient's quality of life and nutritional status as well as patients' adherence and acceptance of the diet. Finally, we plan to re-evaluate patients' dietary habits and clinical outcomes, 6 months after the beginning of the study to address the established dietary adaptations, as well as the sustainability and durability of potential benefits of the dietary intervention.

Design and Methods

The proposed project is a randomized controlled clinical trial which is held in Evangelismos General Hospital of Athensin collaboration with the Department of Food Science & Human Nutrition of Agricultural University of Athens. Briefly, eligible patients are adults with established Crohn's disease with ileal and/or colonic involvement who receive their IBD care at the hospital's Gastroenterology Unit (see eligibility criteria below). Patients with active mild-to-moderate disease, defined by aHarvey–Bradshaw Index (HBI) score of 5–14 points, or inactive disease (HBI<5) are eligible for enrolment. Detailed information about the purpose and the study procedures will be given to all patients and consent form will be signed. The study protocol has been approved by the Ethics committee of the hospital.

Patients will be randomly assigned 1:1 to either CDED plus PEN plus dairy products or PEN plus usual nutritional care. In detail, half of the patients in remission will follow the first stage diet (CDED+PEN) for 4 weeks and will continue with CDED + PEN + dairy products for another 4 weeks. The other half will be given PEN plus the usual advice for a healthy dietary pattern. PEN will cover the 50% of total energy requirements for the first 4 weeks and the 25% during the second 4 weeks. Half of the patients with active disease will follow the first stage diet (CDED + PEN 50%) for 6 weeks and then, the responders will continue with adding the dairy product while PEN will cover 25% of the total energy requirements, for 4 more weeks. The other half will be given PEN plus the usual advice for a low residue diet. Low lactose, low fat and low additive dairy foods will be given, namely Greek yogurt 2% fat and light yellow cheese with 10-12% fat, in calculated portions to meet tailored energy, protein and calcium requirements. After the end of the intervention period, patients will be advised to reintroduce foods that were eliminated and to follow a maintenance diet. All participants will attend study visits at the beginning, in the middle (week 8 or week 10, for patients entering the study in remission or with active symptoms, respectively) and at the end of the study, at which points questionnaires will be completed, anthropometric measurements will be conducted and biological samples will be collected. The last follow-up will take place in week 24. In the meanwhile, phone calls by a researcher dietitian will be held to assess adherence and support the patients.24-hour diet recallsand the modified Medication Adherence Report Scale (MARS) questionnaire (16) will be used to address compliance along with the physician's assessment.

At length, our methodological approach includes:

i) Anthropometry

- (1) Weight (kg) measurement, [Time Frame: Baseline, week 4, week 8 (Baseline, week 6, week 10 for patients entering the study with active disease), week 24]
- (2) Height (m) measurement, [Time Frame: Baseline],
- (3) Body mass index (BMI) (kg/m²) calculation
- (4) Waist, neck and midarm circumferences (cm), triceps skinfold (mm) measurement [Time Frame: Baseline, week 8/w10]
- (5) Body composition analysis (Fat mass, fat %, fat free mass, phase angle)
 by Bioelectrical Impedance Analysis (BIA) [Time Frame: Baseline, week
 8/10]
- (6) Handgrip strength (kg) assessment by dynamometer [Time Frame: Baseline, week 8/w10]
- Dietary habits assessment, using a semi-quantitative food frequency questionnaire (FFQ), to assess dietary habits and adherence to the Mediterranean diet (MD-score) [Time Frame: Baseline, week 24] and 24-

recalls [Time Frame: Baseline, week 2/w3, week 4/w6, week 6/w8, week 8/w10]

- iii) Physical activity assessment, using HPAQ questionnaire [Time Frame: Baseline, week 8/w10]
- iv) Health-related quality of lifeassessment, defined by the selfadministered 32-item Inflammatory Bowel Disease questionnaire (IBDQ) score. Higher IBDQ scores indicate better outcomes. Clinical response defined as increase ≥16 points [Time Frame: Baseline, week 8/w10]
- v) Medical history (e.g.,prior GI surgery, comorbidities) data collection and disease activity assessment by the HBI. Clinical response is defined as baseline HBI score decrease of ≥ 3[Time Frame: Baseline, week 4/w6, week 8/w10]
- vi) **Blood and Feacal samples collection** by specializes staff [Time Frame: Baseline, week 4/w6, week 8/w10]
 - (1) **Blood samples analysis** by the hospital's lab to estimate serum **CRP** and **albumin**
 - (2) Feacal samples analysis by certified labs to estimate Feacal calprotectin concentration (μ g/g)
- vii) Nutrition education according to the intervention principals and prescription of nutritional supplements (liquid formulas-PEN) [Time Frame: Baseline]. Support line for patients' support will be available.
- viii)**Handle-analysis** of the questionnaires and **data entry** in electronic databases [Microsoft® Excel, IBM SPSS Statistics®, Nutritionist Pro®]
- ix) Statistical analysis/interpretation of results.

Eligibility Criteria:

Inclusion Criteria:

- Participants must have an established diagnosis of CD
- Individuals able to give informed consent and willingness to participate Exclusion Criteria:
 - Age < 18 years old
 - Previous extensive bowel resection
 - Reported pregnancy or lactation
 - Current stoma or abscess
 - Clinically significant stricture
 - Introduction of or change in dose of drug therapy within the past 8 weeks

- Comorbidities including diabetes or coeliac disease, or other concomitant serious comorbidity e.g. significant psychiatric, hepatic, renal, endocrine, respiratory, neurological, cardiovascular, neoplastic or other autoimmune disease
- Food allergies or intolerances, which do not permit participation in the study
- Any proven current infection such as positive stool cultures or positive tests for parasites or C. difficile.

The proposed project has a duration of thirty-six (36) months. The 1st phase that has already been completed included preparation and printing of questionnaires, creation of recipes based on the principles of the dietary intervention. The recruitment process is anticipated to start in September 2022 and to be completed by March 2024.

Statistical Analysis Plan (SAP)

Based on pilot data (18) we performed a sample size calculation using the GPower 3.0.10 software (http://www.softpedia.com/get/Science-CAD/G-Power.shtml). A sample of 140 individuals is sufficient to achieve statistical power > 80 %, at a significance level of a = 0,05 for two-sided statistical tests. All continuous variables will be assessed for normality with the Kolmogorov–Smirnov test (cutoff p < 0.01), to use parametric or non-parametric tests, as appropriate. Chi-squared or Fischer's test will be used to analyze categorical variables. Continuous variables will be analyzed by using Mann Whitney U test and t-test for paired-samples or the Wilcoxon signed rank). For paired measures (e.g. FC concentration) before and after the intervention, we will calculate the percentage change for each patient relative to baseline. Logistic regression models will be used to explore how age, sex, phenotypic factors (disease location and activity), MD-scoreat baseline, adherence and intervention grouping would contribute to significant HBI or FC concentration drop.

Bibliography:

3;396(10256):e56]. *Lancet*. 2017;390(10114):2769-2778. doi:10.1016/S0140-6736(17)32448-0

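### The primary goal is a fall in faecal calprotectin, but neither entry nor analysis uses the baseline level, so patients with low baseline values dilute the between-arm contrast

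*Combined protocol and SAP*

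**What the plan says.** - **Goal.** Under Objectives, the primary goal is to find out "whether CDED with PEN could lead to a significant decrease in feacal calprotectin concentration". No size of decrease is given. The same section adds an aim about the proportion of patients whose FC rises significantly after dairy is introduced.
- **Entry.** Design and Methods admits mild-to-moderate active disease (HBI 5–14) "or inactive disease (HBI<5) are eligible for enrolment". The inclusion list asks only for consent and that "Participants must have an established diagnosis of CD". No inclusion or exclusion criterion mentions FC.
- **Measurement.** FC is measured at baseline, week 4 or 6, and week 8 or 10. The plan does not use the baseline value for entry, for stratification or to define an analysis set.
- **Analysis.** For paired measures such as FC, the SAP says "we will calculate the percentage change for each patient relative to baseline". It also plans exploratory logistic models for a significant HBI or FC drop. Their predictors include disease activity, location, adherence and group, but not baseline FC. A significant FC drop is not defined.
- **Sample size.** The SAP states: "Based on pilot data (18) we performed a sample size calculation using the GPower 3.0.10 software". The result is 140 patients for more than 80% power at two-sided 0.05. The Background describes reference 18 as a pilot in mild-to-moderate active disease.

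**The concern.** A decrease can be seen only where there is something to decrease. HBI is a clinical index. Some patients with HBI below 5, and some with symptoms but little intestinal inflammation, may start with FC near the lower limit of the assay. For them a percentage change is largely measurement and day-to-day variation on a small denominator, and the natural question is whether FC stays low. Pooling them with inflamed patients pulls the arms together.

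Two further features add to this. Baseline FC strongly influences how far FC can fall, yet it is in no model, so chance imbalance between arms goes unadjusted. The sample size is drawn from a pilot in active disease, with no stated allowance for patients in remission. At stake is the precision of the main comparison and how a weak or null result could be read.

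**Working it through.** **1. The plan's own figure.** The 140 cannot be reproduced: the SAP gives no endpoint, effect size, SD, response rates or test. It can be back-solved. With 70 per arm, two-sided 0.05 and 80% power:

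d = (1.960 + 0.842) / √(70/2) = 2.802 / 5.916 = 0.474 (0.477 by the t-test).

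A binary equivalent is about 30% versus 53% responders.

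**2. Room to fall.** The largest possible fall is 1 − floor/baseline. Assume a reporting floor of 30 µg/g:
- baseline 40: 1 − 30/40 = 25%
- baseline 60: 1 − 30/60 = 50%
- baseline 100: 1 − 30/100 = 70%

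If a drop means a fall of at least 50%, a measured baseline below 60 cannot qualify. With a floor of 10, a baseline of 40 allows 1 − 10/40 = 75%, and that bar disappears. Neither the floor nor the threshold is in the documents.

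**3. Scenario A: a large effect in inflamed patients.** Assumptions: true FC is log-normal, with median 400 (log-SD 0.7) in inflamed patients and median 40 (log-SD 0.3) in low-FC patients. The diet halves FC in the first group and does nothing in the second. Each measurement carries log-SD 0.4 noise, the floor is 30, and a drop means at least 50%. Simulated drop rates in inflamed patients are 49.9% (diet) and 11.0% (control); low-FC patients reach about 6.3% in either arm, by noise. Mixing with a low-FC share f:

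| f | Diet | Control | Gap (points) |
|---|---|---|---|
| 0 | 49.9% | 11.0% | 39 |
| 25% | 0.75×49.9 + 0.25×6.3 = 39.0% | 0.75×11.0 + 0.25×6.3 = 9.8% | 29 |
| 50% | 0.5×49.9 + 0.5×6.3 = 28.1% | 0.5×11.0 + 0.5×6.3 = 8.7% | 19.4 |

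With 70 per arm, power for the binary comparison is above 99%, then about 98%. At f = 50% it is about 86–87% by simulated chi-squared, and about 92–93% by Mann-Whitney on percentage change. Restricting to baseline FC above 100 at f = 50% raises these to about 94–95% and above 99%.

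**4. Scenario B: 140 gives exactly 80% power undiluted.** Let low-FC patients contribute no effect, with equal SD: d_eff = 0.474 × (1 − f), and power = Φ(d_eff × √35 − 1.96).

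| f | d_eff | Power, all patients | Total N for 80% | Power, raised-FC patients only |
|---|---|---|---|---|
| 0 | 0.474 | 80% | 140 | 80% |
| 25% | 0.355 | 56% | 250 | 68% |
| 50% | 0.237 | 29% | 560 | 51% |

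The last column is Φ(0.474 × √(35(1 − f)) − 1.96).

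Variants at f = 25% and 50%:
- low-FC patients half as variable, simulated t-test: 62% and 41%
- the same, Mann-Whitney: 57% and 32%
- binary endpoint, 30% versus 53.3% undiluted: 61% and 40%, needing about 220 and 380 patients
- equal SD, simulated: 54% and 27% (t-test), 52% and 26% (Mann-Whitney), slightly below the formula

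**5. Does the activity term deal with it?** Activity is defined by HBI. HBI below 5 does not establish low FC, and HBI 5–14 does not establish raised FC. Adjusting for it removes only the part of baseline FC that HBI tracks.

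**The case against.** The strongest reply is that the mixed population is intended. The aim covers both inducing and maintaining remission, the two groups have separate schedules, and the dairy question needs patients in remission. That stands. A reader might infer that enrolling inactive patients is itself the error; the documents do not support that, and nothing here calls for changing who is enrolled.

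A reader might also infer that low-baseline patients cannot show the outcome at all. That holds only under an assumed floor and an assumed threshold. Even in Scenario A, about 21% of low-FC patients have a measured baseline of 60 or more, and about 6% register a 50% drop.

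The FC-drop model is exploratory, and the SAP also plans tests on continuous FC, so counting patients as non-responders does not describe the whole analysis. The model also contains disease activity. Both points are correct, but the percentage-change analysis shares the dilution, and activity is a proxy.

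Finally, the aim on FC elevation after dairy comes close to asking whether FC stays low. However, it is not the primary goal, no between-arm comparison is specified for it, and the control arm is not assigned the dairy step. It does not answer the maintenance question by arm.

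**Conclusion.** The point holds as a matter of dilution and missing baseline adjustment. Its direction is clear; its size is not, because it turns on the low-FC share, the assay floor, the drop threshold and the undiluted effect, none of which the documents give. Scenarios A and B illustrate a wide range: with a large effect, power stays above 80% even when half the patients start low; with an effect only just detectable in 140 patients, a quarter of low-FC patients is enough to bring power to around 60% or below.

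It would be tempting to conclude that the trial will hide a real effect, or that a null result could be put down to who was enrolled. The documents do not support that: Scenario A contradicts it, and Scenario B rests on an assumed calibration. What can be said is that the plan leaves this loss uncontrolled although the variable needed to reduce it is already collected.

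**What to change.** Leave enrolment unchanged and amend the SAP:

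1. Compare follow-up log FC between arms with log baseline FC as a covariate, and add log baseline FC to the logistic model for FC drop. The data are already collected, and there is no material downside beyond one model parameter.
2. Before any outcome data are reviewed, prespecify an analysis of FC decrease in patients whose baseline FC exceeds a stated cut-off, reported alongside the all-patient analysis. State the basis for the cut-off and define a significant FC drop. The cost is fewer than 140 patients and a narrower population. In Scenario B this recovers part of the lost power but does not restore 80%.
3. In patients at or below the cut-off, report by arm the proportion who remain there, in addition to the planned proportion with FC elevation after dairy introduction.

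The sample size paragraph should also state its endpoint, effect and expected share of low-FC patients, so that the remaining loss can be judged. No change to visits, sampling or treatment is needed.

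### Entry HBI group sets the control advice, phase lengths and visit weeks, but the plan neither states how allocation is balanced within the groups nor adjusts the between-arm FC test for them.

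*Combined protocol and SAP*

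**What the plan says.** Under Design and Methods, patients with an HBI "score of 5–14 points, or inactive disease (HBI<5) are eligible for enrolment". Allocation is described in one sentence: "Patients will be randomly assigned 1:1 to either CDED plus PEN plus dairy products or PEN plus usual nutritional care". The text then sets out the two entry groups separately.

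- **Remission (HBI <5).** On the intervention side, "half of the patients in remission will follow the first stage diet (CDED+PEN) for 4 weeks", followed by 4 weeks with dairy. On the control side: "The other half will be given PEN plus the usual advice for a healthy dietary pattern".
- **Active (HBI 5–14).** On the intervention side: "Half of the patients with active disease will follow the first stage diet (CDED + PEN 50%) for 6 weeks and then, the responders will continue". Their second phase adds dairy and lasts 4 weeks. On the control side: "The other half will be given PEN plus the usual advice for a low residue diet".

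The mid-study visit is at "week 8 or week 10, for patients entering the study in remission or with active symptoms, respectively". Intermediate blood, stool and HBI assessments are at week 4 or week 6 in the same way.

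No section names a stratification factor, a block scheme or an allocation list. The SAP gives a single sample size of 140, not divided by entry group. For continuous outcomes it says: "Continuous variables will be analyzed by using Mann Whitney U test and t-test for paired-samples or the Wilcoxon signed rank". Disease activity enters the SAP once, as one of several covariates in logistic models that explore predictors of a significant drop in HBI or FC.

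**The concern.** There are two comparisons under one randomisation. In remission patients, CDED is set against healthy-pattern advice over 4+4 weeks, which is close to a maintenance question. In active patients, it is set against low-residue advice over 6+4 weeks, which is an induction question. The protocol states both aims.

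The description of halves shows that a 1:1 split within each entry group is intended, but a bare 1:1 assignment does not guarantee it. The only between-arm test named for continuous outcomes, which include the FC change named as the primary goal, does not use the entry group.

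Entry group plainly matters for the HBI outcome: response is a fall of at least 3 points, which a patient entering with HBI 0–2 cannot achieve. How strongly it predicts FC change is not given in the documents. If it does predict it, an unadjusted test carries the difference between groups as noise, and any chance imbalance between arms adds to the difficulty of reading the one trial that is run.

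**Working it through.** **Inputs.** From the documents: N = 140, 1:1, two-sided alpha 0.05, power above 80%. Assumed, because not given: the active share s (30%, 50%, 70%), and D, the difference in mean FC change between active and remission entrants in within-group SDs (0.5, 1, 1.5).

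**1. The plan's own figure.** N = 140 cannot be reproduced, because no effect size, SD or rate is stated. Solving backwards with 70 per arm, the standardised difference detectable with 80% power is

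d = (1.960 + 0.842) × √(2/70) = 2.802 × 0.169 = 0.474.

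This is the reference effect below.

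**2. Imbalance if allocation is not stratified.** With arms fixed at 70/70, the number of active patients in one arm is hypergeometric with variance 70 × s(1−s) × 70/139. The SD of the between-arm difference in active share is 2/70 times its square root:

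- s = 50%: (2/70) × √(70 × 0.25 × 0.504) = 8.5 percentage points.
- s = 30% or 70%: (2/70) × √(70 × 0.21 × 0.504) = 7.8 percentage points.

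| Difference in active share | Fixed 70/70 arms | Coin-toss allocation |
|---|---|---|
| 10 points or more | 20–24% of trials | 20–27% |
| 15 points or more | 4–6% | 5–8% |
| 20 points or more | 2–3% | 1–2% |

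**3. What an imbalance does.** A 10-point imbalance moves the unadjusted difference by 0.10 × D. At D = 1 that is 0.10 SD, or 0.10/0.474 = 21% of the detectable effect. On another scale, if FC fell 40% in active and 0% in remission entrants whatever the arm, 10 points would give a ratio of 0.6^0.10 = 0.95. Averaged over randomisations, simulated type I error of the unadjusted t-test was 4.5–5.6%, so there is no systematic bias.

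**4. Power.** In an unadjusted t-type analysis the SD grows to √(1 + D²s(1−s)), so power = Φ(2.802/√(1 + D²s(1−s)) − 1.960). At s = 50%, D = 1: 2.802/1.118 − 1.960 = 0.546, giving 0.71. The Mann-Whitney column is simulated.

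| D | Unadjusted t, s = 50% | Unadjusted t, s = 30% or 70% | Plain Mann-Whitney | Model with stratum term |
|---|---|---|---|---|
| 0.5 | 0.78 | 0.78 | about 0.75 | about 0.79 |
| 1 | 0.71 | 0.72 | about 0.66 | about 0.79 |
| 1.5 | 0.61 | 0.64 | about 0.56 | about 0.79 |

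A little of the Mann-Whitney gap is the price of ranks on normal data. With efficiency 0.955, power at D = 0 is Φ(2.802 × √0.955 − 1.960) = Φ(0.778) = 0.78. A van Elteren test would pay the same small price.

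**5. If allocation is in fact stratified but the test is not.** Imbalance goes, but the unadjusted test still divides by the inflated SD. At D = 1, s = 50%, power is Φ(2.802 − 1.960 × 1.118) = Φ(0.611) = 0.73, and the actual type I error is 2Φ(−2.191) = 0.028. Stratified lists alone therefore do not recover the loss.

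**6. Testing each group separately.** With 35 per arm: Φ(0.474/√(2/35) − 1.960) = Φ(0.02) = 0.51, and the detectable d is 0.67. With 21 per arm (a 30% group): power 0.34, detectable d 0.87.

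**The case against.** Three stronger readings are tempting, and the documents support none of them.

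- **That allocation is a single unstratified list.** The sentences following the 1:1 statement describe half of the remission patients and half of the active patients on the CDED diet. A split within each entry group is a natural reading, and two lists may be what the sponsor has in mind. What can be said is that no method is named.
- **That the plan pools the two groups.** It never says so. The SAP ties no test to a population or visit, and the schedule pairs visits by phase throughout. Pooling is only an inference from the single N and the absence of any by-group analysis.
- **That a chance excess of active patients would pass for a diet effect.** The shift from a 10-point imbalance is small beside the detectable effect, and type I error stays near 5%.

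It is also fair to say that activity is not absent from the analysis: the logistic models include it alongside intervention group, which adjusts the arm effect on a dichotomised HBI or FC drop.

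What remains is that those models are exploratory, do not cover continuous FC change, and include no arm-by-activity term. On either reading of the allocation, the named between-arm test for FC leaves out a factor that defines the control advice and the timetable. Step 5 shows that this costs power even if the lists are stratified.

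**Conclusion.** The point holds as a loss of precision and a gap in specification, not as a source of false-positive findings. If allocation is unstratified and the groups are analysed together, arms would differ by 10 points or more in active share in about 20–27% of trials. The plain Mann-Whitney test would have power of about 0.75, 0.66 or 0.56 where a stratum-adjusted model has about 0.79. The size rests on an assumed active share of 30–70%, an assumed difference of 0.5 to 1.5 SD between the groups in FC change, normal outcomes, and the effect of 0.474 SD back-solved from N = 140. If the groups hardly differ in FC change, almost nothing is lost, and adjustment does no harm. The remedy is nearly free, so it should be adopted whichever assumption is closest.

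**What to change.** 1. **Allocation.** State that randomisation uses two permuted-block 1:1 lists, one for HBI <5 and one for HBI 5–14, with the group fixed by the baseline HBI recorded before assignment.
2. **Main FC comparison.** Make it stratum-adjusted, by a van Elteren test or a model with a stratum term, at the phase-aligned visits (week 4/6 and week 8/10), in place of the plain Mann-Whitney test.
3. **By-group results.** Report each stratum's arm effect as an estimate with a confidence interval. Note that a within-stratum test has only about 50% power with 35 per arm at the effect that N = 140 detects with 80% power, and say which group or groups the 140 is meant to serve.

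The cost is a second list and one SAP sentence, with no added patients, visits or procedures; baseline HBI is already collected. The document is dated August 2022 and recruitment was expected from September 2022, so the lists could be set up before the first assignment. If assignment has already begun, items 2 and 3 can still be adopted before the data are analysed.
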